Investigational Device Exemption for the Revolution™ Peripheral Atherectomy System

Investigator Name

Title

Site Name

Site Number

I have read the protocol and agree that it contains all necessary details for carrying out this study. I will conduct the study as outlined therein.

I will provide copies of the protocol and all information on the device relating to past non-clinical and clinical experience, which were furnished to me by the Sponsor, to all physicians and other study personnel responsible to me who participate in this study, and will discuss this material with them to ensure that they are fully informed regarding the device and the conduct of the study.

I agree to keep records on all subject information (e.g., source documents and informed consent forms), device shipments and return forms, and all other information collected during the study, in accordance with local and national regulations.

Investigator's Signature

Date

SYNOPSIS

Protocol Number:	REX-US-2017-001
Investigational Device:	Revolution™ Peripheral Atherectomy System
Study Title	Revolution™ Peripheral Atherectomy System for Lower Extremity Peripheral Arterial Revascularization (REVEAL)
Sponsor	Rex Medical, L.P. [name]
Study Purpose	To evaluate the safety and effectiveness of the Revolution™ Peripheral Atherectomy System in the treatment of infringuinal lower extremity peripheral arterial occlusive disease.
Study Population	Up to 121 subjects
Number of Sites	Up to 18 investigational sites in the United States
Study Design	A single-arm study of the Revolution™ Peripheral Atherectomy System in subjects with peripheral arterial disease (PAD).
Primary Endpoints	
Primary Safety Endpoint:
 
The primary safety endpoint is freedom from 30-day Major Adverse Events (MAE), defined as the composite of all-cause mortality, clinically-driven target lesion revascularization (TLR), major target limb amputation, major target vessel perforation requiring surgical or endovascular repair and clinically-significant distal embolization in the target limb; as adjudicated by the independent Clinical Events Committee (CEC).
 
Primary Effectiveness Endpoint:
 
The primary effectiveness endpoint is technical success, defined by $\leq 50\%$ diameter stenosis after atherectomy with the Revolution™ Peripheral Atherectomy System and prior to adjunctive therapy, as measured by the independent core laboratory on the post-atherectomy contrast angiogram. Effectiveness will be assessed for investigator-identified target lesions and will be calculated as a binary variable as the proportion of target lesions with technical success.

Secondary Endpoints	The following will be assessed as secondary endpoints of the study: 
1. Change in % stenosis after treatment with Revolution™ Peripheral Atherectomy System, determined after atherectomy and prior to other adjunctive therapies, as measured by the angiographic core laboratory.2. Procedural success as defined by target lesion residual stenosis of $< 30\%$ at the conclusion of the index procedure, after

	
atherectomy and any adjunctive endovascular treatment, as measured by the angiographic core laboratory.
 
3. Assessment of the individual components of the primary safety endpoint (MAE); including all-cause mortality, major target limb amputation, clinically significant distal embolization, major target vessel perforation requiring surgical or endovascular repair, and clinically-driven TLR, measured through 30 days and at 6 months.4. Minor unplanned target limb amputation rate through 30 days and 6 months;5. Myocardial infarction through 30 days and 6 months;6. Incidence of target vessel revascularization (TVR) through 30 days and 6 months;7. Frequency of angiographic procedural distal embolization (symptomatic) in the target limb as confirmed angiographically by the core laboratory;8. Primary patency of the target lesion at 30 days and 6 months, determined by duplex ultrasound or angiography;9. Primary-assisted patency of the target lesion at 30 days and 6 months, determined by duplex ultrasound or angiography;10. Secondary patency of the target lesion at 30 days and 6 months, determined by duplex ultrasound or angiography.
Patient Population	Subjects with symptomatic PAD eligible for treatment with the Revolution™ Peripheral Atherectomy System with atherosclerotic lesions of the superficial femoral, popliteal and tibial arteries will be eligible for inclusion in the study.
Inclusion Criteria	Subjects must meet the following criteria to be included in the study: 
1. Age \geq 18 years;2. Willing and able to provide informed consent;3. Ability to take at least one form of anti-platelet therapy.4. Rutherford Categories 2, 3 or 4 in the target limb; Rutherford category 5 if no exposed bone, tendon or active infection;5. Lesions to be treated with the study device must be located in the same limb;6. Target lesion(s) located within the superficial femoral, popliteal or tibial arteries;7. Target lesion(s) with stenosis $\geq 70\%$ diameter reduction as measured by site-reported angiography;8. Target lesion length(s) ≤ 150 mm;

	
9. Target lesions(s) with reference vessel diameter (proximal and distal to target lesion) ≥ 2.0 mm and ≤ 4.0 mm.

Exclusion Criteria:	
Subjects will be excluded from the study for:
 
1. Subjects in whom amputation above the ankle is necessary, irrespective of the success of revascularization;2. In-stent restenosis within the target lesion;3. Flow-limiting dissection, Type C or greater;4. Target lesions within an autogenous or prosthetic bypass graft;5. History of an endovascular procedure or open vascular reconstruction in the index limb within the last 30 days, including thrombolytic therapy;6. Any open vascular surgical procedure planned in the target limb or endovascular procedures planned in the target vessel within 30 days after the index procedure;7. Kidney disease of sufficient severity, in the Investigator's opinion, to contraindicate lower extremity angiography using standard or alternate contrast agents as per the local Standard of Care;8. Pregnancy or breast feeding. A woman of child-bearing potential must have a negative pregnancy test within one week of index procedure;9. Myocardial infarction or stroke within 2 months of enrollment;10. Contraindication to antiplatelet, anticoagulant, or thrombolytic therapy;11. Uncorrectable bleeding diathesis or platelet dysfunction or thrombocytopenia with platelet count $< 125,000/\mu\text{L}$, known coagulopathy, or INR > 1.5;12. Known allergy to contrast agents or medications used to perform endovascular intervention that cannot be adequately pretreated in the opinion of the investigator;13. History of heparin-induced thrombocytopenia;14. Psychiatric disorder which, according to the investigator, has potential to interfere with provision of informed consent, completion of tests, therapy, or follow-up;15. Clinical/angiographic evidence of distal embolization or acute thrombus;16. Significant stenosis ($>50\%$ diameter reduction) or occlusion of inflow vessels that was not successfully treated ($<50\%$ residual stenosis without flow-limiting dissection) before the study intervention.

Sample Size Calculation	Performance goals of 80% for safety and 76% for effectiveness have been established from prior studies. Enrollment of 121 subjects will provide 90% power, based upon a one-sided 97.5% exact binomial test, an anticipated 30-day MAE rate of 9%, acute technical success of 86%, and a 30-day attrition rate of approximately 10%.
Analytical Sets	The regulatory submission will be based on an approximate sample size of 121 subjects. Assuming a lesion-to-subject ratio of 1.5, approximately 165 target lesions will be evaluable for the primary effectiveness endpoint. Subset analyses will be performed for device effectiveness for superficial femoral/popliteal and tibial artery target lesions.
Pre-Enrollment Testing	Medical history, physical examination with vital signs and directed peripheral vascular examination, laboratory assessment, ankle-brachial or toe-brachial index, and patient-reported outcome measures. The diagnostic angiogram at time of the planned index procedure is performed prior to the point of enrollment in the study; eligibility is, in part, based upon the anatomic findings of the angiogram.
Follow-Up Schedule	Subjects will have required follow-up evaluations at the following time points: 
1. Discharge;2. 1 month post index procedure;3. 6 months post index procedure;
Follow-Up Data Collection	
1. Adverse Events at the index procedure, hospital discharge, and through 6 months;2. Rutherford Category at 1 and 6 months;3. Ankle-brachial or toe-brachial index at 1 and 6 months;4. Duplex ultrasound or angiography of the target vessel at 1 and 6 months.
Clinical Events Committee (CEC)	An independent CEC will review all primary safety endpoint events, unanticipated adverse device effects, and other important safety occurrences as specified in the CEC Charter.
Data Safety Monitoring Board (DSMB)	An independent Data Safety Monitoring Board (DSMB) will review safety data from the study at predetermined time points and as deemed necessary by the Sponsor or the DSMB Chair. The DSMB will make recommendations on protocol modifications and continuation of the study.
Principal Investigator	[name], MD

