7.3. Primary Effectiveness Endpoint

The primary effectiveness endpoint is technical success, defined by $\leq 50\%$ diameter stenosis after atherectomy with the Revolution™ Peripheral Atherectomy System, prior to adjunctive therapy, as measured by the independent core laboratory on the post-atherectomy contrast angiogram. Effectiveness will be assessed for all investigator-identified target lesions in the PP analytic group and will be calculated on a per-lesion basis.

$$H_0: P_E \leq PG_E \text{ versus } H_A: P_E > PG_E$$

for technical success; even though the device performed as designed. Since the eligibility criteria are site-determined, the subject may still be included in the ITT population but the lesion would be excluded from the PP analytic group.

where P_E is the proportion of lesions with technical success, as defined by angiographically-determined $\leq 50\%$ target lesion diameter reduction on the post-atherectomy core laboratory measurement.^g The effectiveness performance goal, PGE, is technical success defined in the same manner, derived from the published literature.

The primary effectiveness endpoint will be calculated for those target lesions that fall at or below the specified acceptable reference vessel diameter of 4.0 mm, as determined by the core laboratory. Target vessels with diameters > 4.0 mm will be excluded from the analysis, since even the largest bit size (2 mm) would not result in a post-atherectomy channel size of $\geq 50\%$ RVD.

The primary effectiveness endpoint analysis will use the E+M approach for one sample correlated binary data with cluster size of one or two that accounts for correlations between multiple target lesions within the same subject.^h

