7.4. Study Success Criteria

The study will be considered a success if both the primary endpoints meet their respective Performance Goals. For the effectiveness endpoint, this translates into observing a one-sided 97.5% lower confidence limit (LCL) of the point estimate above 76% and for the safety endpoint it means observing a one-sided 97.5% LCL above 80%.

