7.9. Sample Size

The PG of 80% has been established for the primary safety endpoint, based on a one-sided 97.5% exact binomial test. The 30-day MAE rate is anticipated to be approximately 9%. Under these assumptions, the required sample size to achieve a level of 90% power is 110 subjects (**Table 4**). Assuming 10% attrition over 30 days, initial enrollment of 121 subjects is necessary.

A PG of 76% has been established for the primary effectiveness endpoint. Anticipating an actual technical success rate of approximately 86%, and based upon a one-sided 97.5% exact binomial test, the required sample size to achieve a level of 90% power is 165 target lesions. Assuming a 1.5 ratio of subjects to treated target lesions, approximately 110 subjects will be necessary (**Table 5**). Since the primary effectiveness endpoint is determined at the time of the index procedure, no attrition has been taken into account.

ⁱ The TALON publication reported the results in 1258 target lesions, among which 132 required preliminary balloon dilatation to deliver the device and technical success ($\leq 50\%$ residual stenosis after atherectomy) was not achieved in 54 lesions. Technical success was calculated assuming there was no overlap between these cases; i.e. technical success was achieved in 1072 (1258 – 132 - 54) lesions.

Table 4. Sample Size – Primary Safety Endpoint

Primary Safety Endpoint	
Performance goal	80%
Anticipated freedom from MAE	91%
Significance level	.025
Statistical test	One-sided exact binomial test
Desired power level	90%
Required sample size prior to 10% 30-day attrition rate	110
Required sample size after attrition adjustment	121

Table 5. Sample Size – Primary Effectiveness Endpoint

Primary Effectiveness Endpoint	
Performance Goal	76%
Anticipated technical success rate	86%
Significance level	.025
Statistical test	One-sided exact binomial test
Desired power level	90%
Required sample size (target lesions)	165
Estimated subjects required for required number target lesions*	110

* Assumes 1.5 target lesions treated per subject; a ratio calculated from the studies in the atherectomy literature review

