3.3 Sample Size Consideration

This study will enroll up to 121 subjects at up to 18 investigational sites and the sample size estimation was based on binomial hypothesis testing of a single proportion.

The performance goal (PG) of 80% has been established for the primary safety endpoint. Sample size estimation was based on a one-sided 97.5% exact binomial test. The 30-day

⁴ This point is defined as entry of the study device into the access sheath/guide at the level where the sheath/guide enters the subject's body.

MAE rate is anticipated to be approximately 9%. Under these assumptions, the required sample size to achieve a level of 90% power is 110 subjects (Table 1). Assuming 10% attrition over 30 days, initial enrollment of 121 subjects is necessary.

A PG of 76% has been established for the primary effectiveness endpoint. Anticipating an actual technical success rate of approximately 86%, and based upon a one-sided 97.5% exact binomial test, the required sample size to achieve a level of 90% power is 165 target lesions. Assuming a 1.5 ratio of subjects to treated target lesions, approximately 110 subjects will be necessary (Table 2). Since the primary effectiveness endpoint is determined at the time of the index procedure, no attrition has been taken into account.

Table 1. Sample Size – Primary Safety Endpoint

Primary Safety Endpoint	
Performance goal	80%
Anticipated freedom from MAE	91%
Significance level	.025
Statistical test	One-sided exact binomial test
Desired power level	90%
Required sample size prior to attrition (subjects) adjustment*	110
Required sample size after attrition rate adjustment	121
*Assumes 10% 30-day attrition	

Table 2. Sample Size – Primary Effectiveness Endpoint

Primary Effectiveness Endpoint	
Performance Goal	76%
Anticipated technical success rate	86%
Significance level	.025
Statistical test	One-sided exact binomial test
Desired power level	90%
Required sample size (target lesions)	165
Estimated subjects required for required number target lesions*	110
*Assumes 1.5 target lesions treated/subject; ratio calculated from atherectomy literature review.	

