4.3 Effectiveness Analyses

The primary effectiveness endpoint is technical success, defined by $\leq 50\%$ diameter stenosis after atherectomy with the Revolution™ Peripheral Atherectomy System, prior to adjunctive therapy, as measured by the independent core laboratory on the post-atherectomy contrast angiogram. Effectiveness will be assessed for all investigator-identified target lesions in the PP analytic group and will be calculated on per-lesion basis.

$H_0: P_E \leq PG_E$ versus $H_A: P_E > PG_E$

Where P_E is the proportion of subjects with technical success, as defined by angiographically-determined $\leq 50\%$ target lesion diameter reduction on the post-

atherectomy core laboratory measurement⁵. The effectiveness performance goal, PG_E, is technical success defined in the same manner, derived from the published literature.

The primary effectiveness endpoint will be calculated for those PP target lesions that fall at or below the specified acceptable reference vessel diameter of 4.0 mm, as determined by the core laboratory. Target vessels with diameters < 2.0 mm and > 4.0 mm will be excluded from the analysis, since even the largest bit size (2mm) would not result in a post-atherectomy channel size of $\geq 50\%$ RVD. For subjects with >1 lesion, it is possible that one vessel qualifies for the PP analysis with RVD ≤ 4.0 mm and others do not, with RVD >4.0 mm. For lesion level effectiveness endpoints, only PP qualifying lesions will be included in the analysis. For subject level effectiveness endpoints, subjects with nonqualifying PP lesion(s) will be excluded from the analysis.

It was originally planned for the primary effectiveness endpoint analysis to use the E+M approach for one sample correlated binary data with cluster size of one or two that accounts for correlations between multiple target lesions within the same subject⁵. However, based on a recommendation from FDA the primary analysis method was changed to generalized estimating equations (GEE). FDA also recommended assessing the power of this analysis using this method, however, it was determined that information needed for the assumptions required was not available, e.g. the correlation between lesions within a subject.

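### The synopsis gives 90% power for 121 subjects without saying that this is a per-endpoint target; power to meet both required endpoints is about 79% to 80% if they are independent, and is stated nowhere

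*Protocol*

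**What the plan says.** - **Synopsis, Sample Size Calculation:** "Enrollment of 121 subjects will provide 90% power, based upon a one-sided 97.5% exact binomial test, an anticipated 30-day MAE rate of 9"%. The same sentence adds 86% technical success and roughly 10% attrition at 30 days. One power figure covers both sets of assumptions.
- **Synopsis, Analytical Sets:** after naming about 121 subjects, "Assuming a lesion-to-subject ratio of 1.5, approximately 165 target lesions will be evaluable for the primary effectiveness endpoint".
- **Protocol 7.9 and Table 4 (safety):** "the required sample size to achieve a level of 90% power is 110 subjects", raised to 121 for attrition.
- **Protocol 7.9 and Table 5; SAP 3.3 (effectiveness):** "the required sample size to achieve a level of 90% power is 165 target lesions". The subject count is then derived from the lesion count: "Assuming a 1.5 ratio of subjects to treated target lesions, approximately 110 subjects will be necessary". The Table 5 footnote makes clear that 1.5 means lesions per subject. No attrition is applied to this endpoint, and no design effect.
- **Protocol 7.4 and SAP 4.5:** "The study will be considered a success if both the primary endpoints meet their respective Performance Goals".
- **Lesions left out of the effectiveness analysis:** Protocol 7.3, "Target vessels with diameters > 4.0 mm will be excluded from the analysis"; SAP 4.3, "Target vessels with diameters < 2.0 mm and > 4.0 mm will be excluded from the analysis".
- **SAP 4.3** also records that the primary effectiveness method became GEE on FDA's recommendation, and that power under GEE was not assessed because the within-subject correlation was not known.

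**The concern.** A single power figure for a single enrolment number is easily read as the chance that the trial succeeds. Here success means passing two tests, and each was given 90% separately. On that reading, the chance of missing the success criterion under the plan's own assumptions would be 1 in 10. If the endpoints are independent it is nearer 1 in 5.

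Two smaller matters affect the figure. Both sample-size tables name an exact binomial test, so the 90% should hold for that test. And the synopsis pairs 1.5 lesions per subject with 121 subjects and 165 lesions, which do not multiply out. A reader therefore cannot tell which lesion count the power rests on.

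**Working it through.** **Inputs** (Protocol 7.9, Tables 4 and 5; SAP 3.3): one-sided α 0.025 for each endpoint; safety 80% against 91%; effectiveness 76% against 86%; 10% attrition for safety; 1.5 lesions per subject.

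**1. The plan's own sizes.** The normal approximation for one proportion is n = [(1.960√(p0(1−p0)) + 1.282√(p1(1−p1))) / (p1−p0)]².
- Safety: [(0.7840 + 0.3668)/0.11]² = 109.4, rounded up to 110.
- Effectiveness: [(0.8371 + 0.4447)/0.10]² = 164.3, rounded up to 165.

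Both tabulated sizes are reproduced.

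**2. Power of the exact test.** Take the smallest count r with P(X ≥ r | p0) ≤ 0.025; power is then P(X ≥ r | p1).

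| Endpoint | n | r | Attained α | Power |
|---|---|---|---|---|
| Safety | 110 | 97 | 0.0170 | 88.2% |
| Safety | 109 | 96 | 0.0189 | 88.8% |
| Effectiveness | 163 | 135 | 0.0227 | 89.8% |
| Effectiveness | 165 | 137 | 0.0187 | 88.5% |
| Effectiveness | 181 | 150 | 0.0163 | 90.4% |

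Exact power is saw-toothed. Between 165 and 181 lesions it runs from 87.9% (at 166) to 92.4% (at 177), so rounded figures are appropriate.

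**3. Counts at 121 enrolled.**
- Safety: 121 × 0.9 = 108.9, about 109.
- Treated lesions: 121 × 1.5 = 181.5, about 181.
- Lesions if 10% attrition also applied: 121 × 0.9 × 1.5 = 163.4, about 163.
- Table 5 works from lesions to subjects: 165 / 1.5 = 110.

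**4. Power to meet both.** If the endpoints are independent, joint power is the product a × b. Under any dependence it lies between a + b − 1 and the smaller of a and b.

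| Subjects / lesions | Independent | Any dependence |
|---|---|---|
| 110 / 165 | 0.8821 × 0.8852 = 78.1% | 76.7% to 88.2% |
| 109 / 165 | 0.8883 × 0.8852 = 78.6% | 77.4% to 88.5% |
| 109 / 181 | 0.8883 × 0.9038 = 80.3% | 79.2% to 88.8% |

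With 109 subjects and every lesion count from 165 to 181, the product runs from 78.1% to 82.1%. The any-dependence limits are 0.8883 + 0.8787 − 1 = 76.7% and 88.8%. Even the nominal targets give only 0.90 × 0.90 = 81%.

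**5. Correlated lesions (illustration only).** The documents give no correlation, mix of one- and two-lesion subjects, or confidence-limit scale, so all three are assumed here. Simulated GEE power for effectiveness, with clusters of one or two, an independence working correlation and robust standard errors:

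| Lesions / subjects | Limit scale | ρ = 0 | 0.2 | 0.3 | 0.5 |
|---|---|---|---|---|---|
| 181 / 121 | logit | 92% | 88% | 86% | 82% |
| 165 / 110 | logit | 89% | 85% | 82% | 78% |
| 181 / 121 | identity | 95% | 92% | 91% | 88% |
| 165 / 110 | identity | 93% | 90% | 88% | 85% |

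The identity-scale limit gains power partly because its one-sided size is about 0.035 to 0.040, against the planned 0.025. The logit-scale size is 0.022 to 0.024.

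**The case against.** Sizing each co-primary endpoint separately is common, and Protocol 7.9, its tables and SAP 3.3 disclose it. The synopsis lists its test, rates and attrition, and nowhere calls the 90% joint power. Exact power of about 88% is within 2 points of the target. Positive association between the endpoints would raise joint power, and with no attrition it would be 81.7% (121/165) or 83.4% (121/181). All of this stands. It limits the fault to the synopsis wording, the 90% claimed for the named exact test, and the absent joint figure.

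Three stronger readings might be inferred, and the documents do not support them:

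- **That the sample-size arithmetic is wrong or the trial too small.** Both sizes reproduce by normal approximation, and no joint-power target was set that 121 subjects fail to meet.
- **That 165 lesions is an error.** The synopsis says approximately and speaks of evaluable lesions. Either 10% attrition (about 163) or the core-laboratory diameter exclusions could account for it. The text does not say which, and Protocol 7.9 applies no attrition to effectiveness. The count is also the lower of the two, so it does not inflate power.
- **That GEE leaves effectiveness underpowered.** SAP 4.3 openly says the needed inputs were missing. The simulated rows show how far power could move, but they rest on assumptions and establish no deficit.

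**Conclusion.** The point holds as a reporting fault. The synopsis attaches 90% to 121 subjects without saying that it is a per-endpoint target, and no section gives power for the criterion that defines success. With 109 subjects evaluable for safety, joint power is about 79% (165 lesions) to 80% (181 lesions). This assumes that the plan's rates hold and that the endpoints, and the lesions, are independent. With that safety count and 165 to 181 lesions, no dependence between the endpoints brings it above about 89%. The chance of missing the success criterion is then at least about 11%, and about 1 in 5 under independence. Positive correlation between lesions in the same subject would lower the effectiveness and joint figures by an amount the documents do not allow anyone to fix. Requiring both endpoints does not inflate type I error, and the tests, success rule and enrolment stand.

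**What to change.** Keep 121 subjects.

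1. In the synopsis, Protocol 7.9 and SAP 3.3, label 90% as a nominal per-endpoint target and add: *With 109 subjects evaluable for safety and 165 to 181 target lesions treated as independent, exact power is about 89% for safety and 88% to 92% for effectiveness. Power to meet both is roughly 80% (78% to 82%) if the endpoints are independent, and about 77% to 89% under any dependence. Positive within-subject correlation between lesions would lower the effectiveness and joint figures.*
2. In the synopsis paragraph on analytical sets, say how about 181 lesions (121 × 1.5) become about 165 evaluable ones. If attrition is the reason, reconcile that with Protocol 7.9, which applies none to effectiveness. If it is the diameter exclusions, state the limits, since Protocol 7.3 and SAP 4.3 word them differently. Then use that one count in the power statement.
3. Optional: beside the SAP 4.3 record of FDA's recommendation, which should stay as it is, add a table of GEE power for assumed within-subject correlations from 0 to 0.5. Give the lesion count, the mix of one- and two-lesion subjects and the confidence-limit scale as assumptions.

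The cost is a few sentences and, if wanted, one small simulated table. The downside is that the stated power becomes less favourable.

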6.5. Study Populations

The point of enrollment in this study occurs when a study device first enters a subject's vasculature.^e The following populations will be analyzed in the study:

Intention to treat (ITT) analysis: The ITT analysis will be performed on all enrolled subjects in whom the study device entered the vasculature, irrespective of adherence with the entry criteria, treatment actually received, subsequent withdrawal, or deviation from the investigational plan.²⁴

Per Protocol analysis: The PP analysis will be performed on target lesions with core laboratory-determined RVD falling within the pre-specified anatomic eligibility criteria of ≤ 4.0 mm. The effectiveness endpoints will be determined using the PP analytic subset to exclude lesions where the largest bore (2.0 mm) study device is less than 50% of the RVD (see Section 7.3, page 22, below).^f

^e This point is defined as entry of the study device into the access sheath/guide at the level where the sheath/guide enters the subject's body.

^f Use of the 2.0 mm bore in a vessel larger than 4.0 mm in diameter would not result in a lumen channel that exceeds 50% of the RVD. In other words, the residual stenosis after successful atherectomy would still not meet the criteria

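### The synopsis gives 165 evaluable lesions for 121 subjects where its own ratio gives 181.5, and the 165-lesion requirement has 88.5% exact power and states no allowance for the RVD exclusion

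*Protocol*

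**What the plan says.** The protocol synopsis, under Analytical Sets, gives an approximate sample size of 121 subjects and then states: "Assuming a lesion-to-subject ratio of 1.5, approximately 165 target lesions will be evaluable for the primary effectiveness endpoint".

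Protocol 7.9 derives the lesion count. The inputs are "A PG of 76% has been established for the primary effectiveness endpoint" and "Anticipating an actual technical success rate of approximately 86" per cent. The result is: "based upon a one-sided 97.5% exact binomial test, the required sample size to achieve a level of 90% power is 165 target lesions". The conversion to subjects reads: "Assuming a 1.5 ratio of subjects to treated target lesions, approximately 110 subjects will be necessary". The note to Table 5 gives the source of the ratio: "Assumes 1.5 target lesions treated per subject; a ratio calculated from the studies in the atherectomy literature review". On losses, 7.9 says: "Since the primary effectiveness endpoint is determined at the time of the index procedure, no attrition has been taken into account". SAP 3.3 and its Table 2 repeat the derivation. The 121 arises separately, from the safety endpoint: 110 subjects raised for 10% attrition over 30 days.

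The primary effectiveness analysis uses the per-protocol lesion set. Protocol 6.5 says: "The PP analysis will be performed on target lesions with core laboratory-determined RVD falling within the pre-specified anatomic eligibility criteria of" at most 4.0 mm. Protocol 7.3 excludes target vessels above 4.0 mm. SAP 4.3 excludes those below 2.0 mm as well as those above 4.0 mm. Protocol 9.3 says that eligibility rests on site measurements and not on core-laboratory values.

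**The concern.** The three synopsis figures (121 subjects, ratio 1.5, 165 lesions) do not multiply out. Attrition cannot bridge the gap, because 7.9 applies none to this endpoint.

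The reason given for applying none covers loss to follow-up only. It does not cover the removal of lesions by core-laboratory RVD, which is measured on the angiogram from that same procedure. Because sites enrol on their own readings, the footnote to protocol 6.5 itself foresees enrolled subjects whose lesions leave the per-protocol set.

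Power for effectiveness depends on the number of evaluable lesions, while enrolment is capped in subjects, at up to 121. The study succeeds only if both primary endpoints meet their goals. A reader therefore needs to know how many evaluable lesions 121 subjects should yield and what power that gives. The documents answer neither question consistently.

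**Working it through.** **Inputs.** Goal p0 = 0.76, anticipated rate p1 = 0.86, one-sided 0.025, exact binomial test, 90% power, 165 lesions, 1.5 lesions per subject, 110 subjects (protocol 7.9 and Table 5; SAP 3.3 and Table 2). Enrolment 121 (synopsis). No document gives an RVD exclusion rate, so the rates below are assumptions.

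**1. Reproducing 165.** Normal approximation with null and alternative variances:

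n = [(1.960 x sqrt(0.76 x 0.24) + 1.2816 x sqrt(0.86 x 0.14)) / 0.10]^2 = [(0.8371 + 0.4447) / 0.10]^2 = 164.3, so 165.

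Then 165 / 1.5 = 110 subjects. The plan's figures reproduce by this method.

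**2. The test that the plan names.** The exact test rejects at the smallest k for which P(X >= k | n, 0.76) <= 0.025; power is P(X >= k | n, 0.86).

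| Lesions | Reject at | Exact alpha | Exact power |
|---|---|---|---|
| 165 | >= 137 | 0.0187 | 88.5% |
| 166 | >= 138 | 0.0169 | 87.9% |
| 167 | >= 138 | 0.0246 | 91.1% |
| 176 | >= 146 | 0.0165 | 89.6% |
| 177 | >= 146 | 0.0238 | 92.4% |
| 181 | >= 150 | 0.0163 | 90.4% |
| 182 | >= 150 | 0.0233 | 93.0% |

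Exact power rises in a sawtooth. It first reaches 90% at 167 and stays at or above 90% from 177.

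**3. The synopsis product.** 121 x 1.5 = 181.5, whereas 110 x 1.5 = 165. Obtaining 165 from 121 subjects needs a ratio of 165 / 121 = 1.36. The surplus is 181.5 - 165 = 16.5 lesions, and 16.5 / 181.5 = 9.1%.

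**4. The ratio.** Five studies appear in both protocol Table 2 (subjects) and Table 3 (lesions). Lesions over subjects: 89/89 = 1.00; 123/105 = 1.17; 164/161 = 1.02; 131/84 = 1.56; 1258/601 = 2.09. The unweighted mean is 1.37. Pooled, 1765/1040 = 1.70.

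**5. Power with 121 subjects.** Evaluable lesions = 121 x ratio x (1 - exclusion), rounded down; lesions independent.

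| Ratio | Assumed exclusion | Lesions | Reject at | Exact power |
|---|---|---|---|---|
| 1.50 | 0% | 181 | >= 150 | 90.4% |
| 1.50 | 5% | 172 | >= 142 | 91.8% |
| 1.50 | 10% | 163 | >= 135 | 89.8% |
| 1.50 | 15% | 154 | >= 128 | 87.3% |
| 1.50 | 20% | 145 | >= 121 | 84.3% |
| 1.37 | 0% | 165 | >= 137 | 88.5% |
| 1.37 | 20% | 132 | >= 111 | 78.0% |
| 1.70 (1765/1040) | 0% | 205 | >= 169 | 93.8% |
| 1.70 (1765/1040) | 20% | 164 | >= 136 | 89.1% |

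The 5% row exceeds the 0% row at a ratio of 1.5 because of the sawtooth: the attained alpha is 0.0242 at 172 lesions and 0.0163 at 181.

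**The case against.** The strongest defence is that the design calculation is sound and only one synopsis sentence is loose. The 165 follows from its inputs by a standard approximation, and dividing by 1.5 gives 110. The synopsis error is conservative, since 121 subjects at 1.5 yield more lesions than stated. The extra 11 subjects enrolled for safety serve effectiveness too, and at an assumed 10% exclusion power is still 89.8%. All of this stands, and it limits the point to stated figures.

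It does not remove the point. No document says that the extra subjects are meant to absorb RVD exclusions, and the named exact test does not give 90% at 165. Reading evaluable as after 10% attrition would give 121 x 0.9 x 1.5 = 163, close to 165, but 7.9 rules out attrition for this endpoint.

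A reader might also infer that 1.5 is wrong because the tables do not return it. The documents do not support that. The note credits a review of 19 studies, only five of which show both counts in the tables. The 1.5 lies between 1.37 and 1.70. A sixth study, an early series whose title in the reference list gives 60 patients, has 86 lesions in Table 3: 86/60 = 1.43. Dropping the 601-subject registry lowers the pooled ratio to 507/439 = 1.15, but nothing in the documents justifies leaving out the largest study.

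**Conclusion.** The point holds as an error in stated figures. The synopsis pairs 121 subjects with the lesion count for 110, a difference of 16.5 lesions. The stated 90% at 165 lesions is 88.5% under the named test. The no-attrition statement overlooks a lesion exclusion that the plan itself prescribes, and no rate is given for it.

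A reader might go further and conclude that the trial is underpowered, or that it has no lesions to spare for the exclusion. Neither follows. At 1.5 lesions per subject, 121 subjects leave 165 lesions after about 9% exclusion. A shortfall below 165 needs a ratio under about 1.36 or a higher exclusion rate. The 1.5 is unverifiable from the tables, which is a gap in transparency and not a demonstrated error.

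These powers assume the 86% success rate and independent lesions. SAP 4.3 has replaced the E+M method with generalized estimating equations and says that the within-subject correlation needed for a power assessment was not available. Positive correlation between lesions in the same subject would lower the effective number of lesions, so the figures are more likely to be high than low. The exclusion rates are assumptions.

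**What to change.** - **Synopsis, Analytical Sets:** state 181 to 182 lesions for 121 subjects, or tie 165 explicitly to 110 subjects.
- **Protocol 7.9 and Table 5; SAP 3.3 and Table 2:** restate the exact power at 165 lesions as 88.5%. Replace the no-attrition sentence with: evaluable lesions = 121 x ratio x (1 - RVD exclusion).
- **Exclusion rule:** use the same RVD bounds in protocol 7.3 and SAP 4.3, and state an expected exclusion rate with its basis.
- **Power table:** show exact power for ratios on both sides of 1.5 (for example 1.37 to 1.70) and assumed exclusions of 0 to 20%, and note that lesions are treated as independent.
- **Ratio:** name the studies behind 1.5 and show the calculation. Correct the reversed wording in 7.9 and SAP 3.3, which describes it as subjects to lesions when lesions per subject is meant.

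The cost is a text revision of both documents and a slightly less favourable stated power. No extra subjects are needed.
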